 1. HIV-I & II, HCV, HBV, B19, HAV
 2. Adverse events and Concomitant Meds
- Complete all Visit 9 study activities described above
- Subjects will not attend Visit 10 and Visit 11
- Complete all Visit 12 study activities
- Complete all Visit 13, 14, and 15 study activities (optional)

Patients who convert to Alzheimer Disease will be followed for safety reasons, to determine rate of conversion between groups, and to track any continued changes in ventricular volume between the 0.4 g/kg NewGam or 0.9% saline solution (placebo) groups.

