In July 2009, Fillit et al [10] published a retrospective analysis of the risk of AD and related disorders in people ≥ 65 with a prior history of one or more IVIG treatments for indications other than AD. Cases were matched to controls on age, gender, and risk factors for AD and related disorders. This study analyzed an approximate 4-year period and demonstrated that previous treatment with IVIG was associated with a 42% lower risk of developing AD and related disorders.

The potential protective effect of IVIG against AD could best be utilized in persons identified to be at greatest risk for developing AD prior to the development of advanced disease and neuropathology. Persons with a-MCI have been identified a group at high risk of progressing to AD with a conversion rate of approximately 15% per year. [11, 12] Vermuri used data from the Alzheimer Disease Neuroimaging Initiative including CDR-SB and MMSE to assess disease progression (while investigating potential biomarkers, MRI and CSF) of AD and demonstrated that 60 of the 192 subjects with a-MCI converted to AD over 1.5 years; i.e., annual conversion rate from a-MCI to AD of 20.8% [13].

This study will investigate treating persons with a-MCI with IVIG (NewGam 10%) 0.4g/kg every 14 days over the course of three months with the intent of showing differences in brain MRI volume, cognition, and conversion to AD when compared with placebo after 24 months. We chose this dose of IVIG based on recent evidence from Relkin [8] who showed that this may be an optimal IVIG dose for reduction of brain atrophy in patients with AD. Furthermore, Fillet [10] demonstrated a lower risk of AD in patients who had received only one treatment of IVIG.

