2.4 Secondary endpoints

- Conversion from a-MCI to AD as measured by NINCDS-ADRDA, National Institute on Aging (NIA) criteria for diagnosis of Alzheimer Disease, [14] and Clinical Dementia Rating (CDR)
- Change in ventricular volume as measured by MRI at baseline, 12 months, 24 months, 36 months, 48 months, and 60 months following infusion of either 0.4 g/kg NewGam or 0.9% saline solution (placebo) every 14 days x 5 in patients with positive CSF A β 1-42/CSF P-Tau_{181P} Alzheimer signature
- Change in cognitive performance between baseline and 4, 8, 12, 16, 20, 24, 36, 48, and 60 months after the first infusion as measured by: Alzheimer Disease Assessment Scale-cognitive subscale (ADAS-cog)
- Mini Mental State Exam (MMSE)
- Clinical Dementia Rating (CDR) and Sum of Boxes (CDR-SB)

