7.5 VISIT 8: Month 8 (± 7 days)

- Assess and record AEs
- Record concomitant medications
- Record vital signs
- Perform physical and neurological examinations
- Administer MMSE, ADAS-Cog, and CDR-SB
- Obtain blood sample for HIV-I & II, HCV, HBV, B19, HAV

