7.7 VISIT 10: Month 16 (± 7 days)

- Assess and record AEs
- Record concomitant medications
- Record vital signs
- Perform physical and neurological examinations
- Administer MMSE, ADAS-Cog, and CDR-SB

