7.8 VISIT 11: Month 20 (± 7 days)

- Assess and record AEs
- Record concomitant medications
- Record vital signs
- Perform physical and neurological examinations
- Administer MMSE, ADAS-Cog, and CDR-SB

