8.0 CONVERSION TO ALZHEIMER DISEASE

Patients who convert to AD will have the choice of remaining in the study on a modified follow-up visit schedule, or may withdraw from the study. Depending on when the conversion occurs, the subjects will be asked to complete the following:

- Complete all Visit 7 study activities described above
- Complete only the following for Visit 8:

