15.2.2 Cognitive change

The CDR-SB, MMSE, and ADAS-cog are administered at baseline and at months 4, 8, 12, 16, 20, 24, 36, 48, and 60. Separate linear mixed-effects modeling will be used to compare differences in the scores on each these tests using all available observations. Treatment (IVIG/placebo), MCI status (early, late), and treatment X MCI status will be fixed factors and the respective baseline score will be included as the continuous covariate. For statistically significant ($p < 0.05$), interactions, MCI status will be stratified and the analyses will be conducted for each stratum.

Data will be analyzed to assess safety after 25 subjects complete three months of follow-up. Safety will be evaluated through documentation of adverse events. Appropriate safety data summaries will be provided to the DSMC after each interim analysis.

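### Section 8.0 withholds cognitive tests at months 8, 16 and 20 from known converters to AD, so the section 15.2.2 model may understate a cognitive benefit if IVIG delays conversion

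*Combined protocol and SAP*

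**What the plan says.** Section 8.0 lets a subject who converts to AD stay in the study on a reduced schedule, or leave. For month 8 the instruction is "Complete only the following for Visit 8", followed by infection serology and a review of adverse events and concomitant medications. MMSE, ADAS-cog and CDR-SB are not on that list. The section then adds "Subjects will not attend Visit 10 and Visit 11". Sections 7.5, 7.7 and 7.8 place Visits 8, 10 and 11 at months 8, 16 and 20, with all three cognitive tests. Converters keep the full content of Visits 7, 9 and 12 (months 4, 12 and 24), cognition included. Their extension visits are optional.

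Section 2.4 defines the endpoint as "Change in cognitive performance between baseline and 4, 8, 12, 16, 20, 24, 36, 48, and 60 months after the first infusion". Sections 12.0 and 15.2.2 repeat those months, and none of the three mentions converters. Section 15.2.2 fits a linear mixed model to each scale "using all available observations", with treatment, MCI status, their interaction and the baseline score. It states no visit or time term, covariance structure, missing-data assumption or sensitivity analysis.

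**The concern.** Whether a subject is tested at months 8, 16 and 20 depends on an outcome. Under section 15.2.1 conversion is judged partly on the CDR, which is itself one of the cognitive measures. The planned gaps therefore fall on the subjects who have declined most.

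If IVIG delays conversion, more placebo than IVIG subjects are missing at these visits, and the remaining placebo subjects look better than the whole arm. A model without a visit term pools all post-baseline scores into one treatment coefficient. It then gives too little weight to the late scores of the worst decliners. At stake is the size of a real cognitive benefit in a trial with 25 subjects per arm.

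**Working it through.** **1. The plan's conversion rates.** Section 1.0 gives a "conversion rate of approximately 15% per year" and a second figure of 60 conversions in 192 subjects over 1.5 years. The second reproduces: 60/192 = 31.25%, and 31.25%/1.5 = 20.8% per year. The plan gives no effect size or power for cognition, so there is no cognitive figure to reproduce.

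**2. Who is untested.** A subject skips a visit's tests only if conversion was found at an earlier visit. The skipped fraction is 1 - (1 - r)^(m/12), where m is the preceding visit, assuming no other dropout.

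| Visit skipped | m | r = 15% | r = 20.8% | Of 25 placebo subjects |
|---|---|---|---|---|
| Month 8 | 4 | 5.3% | 7.5% | 1.3 to 1.9 |
| Month 16 | 12 | 15.0% | 20.8% | 3.8 to 5.2 |
| Month 20 | 16 | 19.5% | 26.7% | 4.9 to 6.7 |

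With equal rates in both arms, the counts among 50 subjects are 2.6-3.7, 7.5-10.4 and 9.7-13.4. They sum to about 20 to 27 of the 50 x 6 = 300 planned post-baseline assessments to month 24 (6.6% to 9.2%).

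**3. Effect on the estimate.** The documents give no trajectories, so two families were simulated. Both use assumed slopes and SDs, both omit the MCI terms, and each compares fits with and without the section 8.0 gaps.

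*Linear decline* (CDR-SB-like scale, random intercept and slope, conversion when the observed score crosses a threshold, 2,000-3,000 per arm, 3 replicates):
- Random-intercept model with the section 15.2.2 terms: -0.425 becomes -0.408 (4%) and -0.399 becomes -0.379 (5%), with 24-month placebo conversion of 26% and 35%. With 62% conversion, -0.562 becomes -0.508 (10%).
- Model with visit, treatment-by-visit and random slope: the average is -0.399 with or without the gaps. In the 62% case it moves from -0.562 to -0.558 (under 1%). Month 20 stays within about 3% and month 24 is unchanged.
- Raw observed difference at month 20: 23-28% smaller with 26-36% conversion, and 36-43% smaller with 49-62%. At month 8 it is 1-6% smaller.

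*Accelerating decline* (ADAS-cog slope of 1 point per year, rising to 6 from six months before conversion; 20.8% per year on placebo; hazard 42% lower on IVIG, borrowed from the retrospective study in section 1.0):
- Section 15.2.2 terms: 0.475 becomes 0.375 (0.100/0.475 = 21%). Repeat runs with other assumed SDs lost between 13% and 20%.
- Full visit model: in one run the average fell from 0.58 to 0.53, with losses of about 25% at month 16 and 18% at month 20. Another run lost about 14% at both months.
- Raw observed difference: 0.57 becomes 0.13 at month 16, and 0.82 becomes 0.18 at month 20. Month 24 is unchanged.

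**4. No true effect.** Under linear decline with equal arms, the coefficient was -0.022 without the gaps and -0.021 with them. No bias was detectable in any model.

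**5. Using only visits scheduled for everyone.** Under accelerating decline, the section 15.2.2 terms fitted to months 4, 12 and 24 gave 0.467 against a full-data 0.475, 0.58 against 0.58, and 0.455 against 0.52. The average is over different months, so close agreement is reassuring but is not recovery of the same quantity. Testing converters at Visit 8 alone did not reduce the pooled bias.

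**The case against.** The strongest reply is that a likelihood-based mixed model already handles such gaps. Converters are tested at the visit where conversion is found and, if they stay, at months 12 and 24. Because the skip is triggered partly by recorded scores, missing at random is plausible. This stands for a model with visit, treatment-by-visit and a suitable covariance when decline is roughly linear. Section 15.2.2 does not specify that model, and with accelerating decline even that model did not fully recover months 16 and 20.

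A second reply is that section 8.0 follows converters for safety, conversion rate and ventricular volume, not cognition, and that cognition is an unpowered secondary endpoint in a study section 17.0 calls exploratory. That explains the lighter schedule and limits the weight of the point. It does not explain why sections 2.4, 12.0 and 15.2.2 still list the dropped months without exception.

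A reader might go further and infer that these visits measure only non-converters, that the effect is certain to be shrunk, or that cognition at months 16 and 20 cannot be studied at all. The documents do not support this. A subject first diagnosed at Visit 8, 10 or 11 attends that visit and is tested. Cumulative conversion by months 16 and 20 (5-8 of 25 placebo subjects) therefore overstates the number untested. Shrinkage also needs a real effect on conversion. Raw visit means are distorted, but they are not the planned analysis.

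**Conclusion.** The conflict between section 8.0 and sections 2.4, 12.0 and 15.2.2 is certain, and so is the outcome-dependent missingness at months 8, 16 and 20. The consequence is conditional: the model as written may understate a cognitive benefit if IVIG delays conversion.

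A fair range for the loss on the pooled coefficient is about 4-21%. The low end comes from linear decline, and the high end from an assumed six-fold acceleration for which the documents give no basis. With linear decline and a full visit model the loss is about 0-1%. Month 24, the horizon of the primary objective, is unaffected for subjects who remain. Two matters were not examined: the MCI terms, which Amendment 8 links to conversion, and optional withdrawal after conversion, which could add bias. The point is worth acting on because the main remedy is a change of wording; confidence is high on the mechanism and moderate on its size.

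**What to change.** In section 15.2.2:
- Add visit and treatment-by-visit terms, and state the covariance structure and the missing-data assumption.
- Compare arms at visits scheduled for every subject: months 4, 12 and 24, with month 24 as the main contrast, and the extension visits for those who continue.
- Report months 16 and 20 as descriptive or sensitivity results, noting that known converters are absent.

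Reconcile section 8.0 with sections 2.4, 12.0 and 15.2.2, so that each says which cognitive visits apply after conversion.

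As a minor addition, give converters the three tests at Visit 8, which they already attend. This fills the month 8 gap for subjects who have not yet passed it, but does not by itself remove the bias. Without it, month 8 should be handled like months 16 and 20.

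The cost is a small loss of precision from setting aside some non-converter scores, a comparison that no longer averages over every visit, and one test session at a visit already scheduled.

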7.6 VISIT 9: Month 12 (± 7 days) - 12 months after baseline

- Assess and record AEs
- Record concomitant medications
- Record vital signs
- Obtain a brain MRI according to Appendix E for clinical assessment, ventricular volume, and review the scan for evidence of vasogenic edema, microhemorrhage, infarction or other clinically significant abnormality
- Perform physical and neurological examinations
- Administer MMSE, ADAS-Cog, and CDR-SB
- Obtain blood sample for routine hematology and chemistry laboratory tests

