10.7 Reporting of adverse drug reactions and other safety information to study supporter

All suspected AEs and other safety information associated with the administration of NewGam have to be reported to:

Email: [contact]

[contact]

Serious adverse drug reactions have to be reported immediately by fax or email (within 24 hrs). Non-serious adverse drug reactions and other safety information should be reported to Octapharma, if possible, upon recognition but no later than 10 days.

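### Converters skip Visits 10 and 11 with no substitute AE or medication check, so conversion by Month 12 leaves 12 months between scheduled checks instead of 4

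*Combined protocol and SAP*

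**What the plan says.** Section 8.0 lets a subject who converts either withdraw or stay on a modified schedule. The list is conditional: "Depending on when the conversion occurs, the subjects will be asked to complete the following". It keeps Visit 7 (Month 4), Visit 9 (Month 12) and Visit 12 (Month 24) in full. It cuts Visit 8 (Month 8) to viral serology, AEs and concomitant medications, and makes the extension visits optional. For Months 16 and 20 it says "Subjects will not attend Visit 10 and Visit 11" and names no call, informant contact or other check. The section ends with its reasons: "Patients who convert to Alzheimer Disease will be followed for safety reasons, to determine rate of conversion between groups", and to track ventricular volume.

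For everyone else, Sections 7.7 and 7.8 (Visits 10 and 11) list an AE assessment and the item "Record concomitant medications". Section 6.11 ties medication review to study visits, so a skipped visit is a skipped check. Section 10.1 counts AEs from randomisation to the end of the study. Section 6.11 also prohibits cholinesterase inhibitors, memantine and similar agents unless the investigator approves. Section 8.0 does not say whether that still applies after conversion.

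**The concern.** Two things are at stake.

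First, how often a subject is asked about AEs in Months 13 to 24 depends on conversion. Conversion happens after randomisation and is a secondary endpoint compared between arms (Sections 2.4 and 15.2.1). If treatment changes the conversion rate, the arm with more conversions gets fewer scheduled checks, and fewer AEs may be recorded there. If IVIG lowered conversion, placebo AEs would be the more likely to go unrecorded and IVIG would look relatively less safe. If it raised conversion, the reverse would hold.

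Second, an AD drug started after Month 12 would first be asked about at Month 24, the visit with the MRI and cognitive tests. Its start date might have to be recalled over as much as a year, which makes it harder to judge how much drug exposure lies behind the Month 24 values. That newly diagnosed subjects are likelier to start such drugs is a plausible inference; the documents do not say so.

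**Working it through.** The plan gives no figure for this gap, so there is none to reproduce. The upper conversion rate checks: Section 1.0 reports 60 of 192 over 1.5 years as an "annual conversion rate from a-MCI to AD of 20.8" percent, and 60 / 192 / 1.5 = 0.208.

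**Interval between scheduled AE and medication checks, Months 12 to 24**

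| Conversion diagnosed | Visits attended | Longest interval | Checks lost |
|---|---|---|---|
| Not converted | 9, 10, 11, 12 | 4 months | 0 |
| By Visit 9 (Month 12) | 9, 12 | 24 − 12 = 12 months | 2 |
| At Visit 10 (Month 16) | 9, 10, 12 | 24 − 16 = 8 months | 1 |
| At Visit 11 or later | 9, 10, 11, 12 | 4 months | 0 |

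With the ±7 day windows, the 12-month interval can reach 12 months plus 14 days. In Months 13 to 24 a subject who converts by Month 12 has one scheduled check against three.

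**Inputs for the expected loss**
- 25 subjects per arm (Section 3.1).
- Annual conversion r = 15% or 20.8% (Section 1.0).
- Hazard ratio HR = 1 (no effect), or 0.58 in the IVIG arm. The 0.58 is an assumption: it takes the 42% lower risk in the retrospective study cited in Section 1.0 and applies it as a hazard ratio for conversion.
- No withdrawals, and conversion established at scheduled visits.

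**Formulas**
- Probability of conversion by t years: P(t) = 1 − (1 − r)^(t × HR).
- Expected checks lost per arm = 25 × [2 × P(12 months) + (P(16 months) − P(12 months))].

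**Results**

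| r | HR | Converted by Month 12, of 25 | Converted by Month 16, of 25 | Checks lost per arm | Share of the 50 planned at Visits 10 and 11 |
|---|---|---|---|---|---|
| 15% | 1 | 3.75 | 4.87 | 2 × 3.75 + 1.12 = 8.62 | 17.2% |
| 20.8% | 1 | 5.20 | 6.68 | 2 × 5.20 + 1.48 = 11.88 | 23.8% |
| 15% | 0.58 | 2.25 | 2.95 | 2 × 2.25 + 0.70 = 5.20 | 10.4% |
| 20.8% | 0.58 | 3.16 | 4.13 | 2 × 3.16 + 0.97 = 7.29 | 14.6% |

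- Converters by Month 12 over both arms, no effect: 50 × 0.15 = 7.5 to 50 × 0.208 = 10.4.
- Difference between arms at HR 0.58: 8.62 − 5.20 = 3.4 checks to 11.88 − 7.29 = 4.6 checks, or about 7 to 9 percentage points of the Visit 10 and 11 checks.
- Against all 150 checks planned per arm at Months 4 to 24 (25 × 6), the no-effect loss is 8.62 / 150 = 5.7% to 11.88 / 150 = 7.9%.

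**Time since treatment.** The last infusion is Day 56 (Section 7.3). Month 12 is about Day 365, so the gap opens 365 − 56 = 309 days, about 10 months, after it. At the 9.3-day half-life cited in Section 17.0, that is 309 / 9.3, about 33 half-lives.

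**The case against.** The case for leaving the schedule alone is substantial.

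- **Drug safety.** The gap opens long after the last infusion. Viral serology ends at Month 8, and Visits 10 and 11 carry no ECG, MRI or laboratory test for anyone, so converters lose none. This stands, and it limits the safety consequence.
- **Spacing.** All subjects move to 12-month visits after Month 24. True, but that spacing does not depend on conversion; the Month 12 to 24 gap does.
- **Analysis.** No between-arm AE test is planned. Section 15.2.2 evaluates safety through documentation of AEs, and its planned safety review falls at three months of follow-up. No planned analysis uses medication start dates. This stands, and the imbalance is small and needs a treatment effect on conversion to arise at all.
- **Burden.** A lighter schedule may keep converters who would otherwise withdraw. Fair, but a short call costs them little.
- **Visit 8.** Its AE check accompanies a blood draw, so it does not prove that a safety-only contact was thought workable. It does show that the section can state a reduced check.
- **Timing.** Amendment 8 already reports year-2 conversions, so many Month 16 and 20 visits may be past. The documents do not settle how many.

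A reader might infer more than the text supports. Not every converter has a 12-month gap. AE collection does not stop: Section 10.1 runs to the end of the study and Section 10.5 requires patient-reported AEs to be recorded. Section 8.0 does not flatly contradict its safety purpose, since the Month 12 and 24 safety visits are kept. The 24-hour rule in Section 10.7 governs how fast serious drug reactions are reported to the supporter. It is not tied to visits, and subjects seen every four months are in the same position, so it lends no support. That converters recall events worst is also not in the documents: all subjects have amnestic impairment at entry, and Section 4.1 requires an informant in contact with the subject at least twice a month. That informant's duty is toward the subject, however, and creates no scheduled report to the site.

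**Conclusion.** The point holds in limited form. Section 8.0 drops two scheduled AE and medication checks for subjects who convert by Month 12, one for those who convert at Visit 10, and none for later converters, with nothing in their place. What lapses is scheduled detection; the obligation to record AEs continues. The weight lies on two things: ascertainment that depends on an outcome compared by arm, and AD drug starts first asked about at Month 24.

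The sizes rest on the protocol's background rates, constant hazards and no withdrawals, and the between-arm difference rests on the assumed hazard ratio. Actual conversion may be lower: Amendment 8 reports none at year 1 in early MCI and does not report late MCI. Grade: optional, cheap improvement.

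**What to change.** Replace the Visit 10 and 11 bullet in Section 8.0 with one stating that, at Months 16 and 20, converters have AEs and concomitant medications collected only, by telephone with the subject and informant. The same section should state whether the Section 6.11 restriction still applies after conversion, so that the two can be read together.

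The cost is one bullet and roughly 15 to 24 short calls in total: 7.5 × 2 = 15 for Month 12 converters alone at the lower rate, and 11.88 × 2, about 24, with Visit 10 converters included at the upper rate. At HR 0.58 in the IVIG arm the total would be 8.62 + 5.20 = 13.8 to 11.88 + 7.29 = 19.2. There is a small added burden on converters and informants, but no clinic attendance, procedure or new staff.

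If these visits are already past, what can still be done is reporting: give the number of Visit 10 and 11 checks missed through conversion, by arm, beside the AE summary for Months 13 to 24.

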9.0 WITHDRAWAL AND REPLACEMENT OF SUBJECTS

9.1 Criteria for subject withdrawal

In accordance with the Declaration of Helsinki and other applicable regulations, a subject has the right to withdraw from the study at any time and for any reason. If a subject requests or decides to withdraw, every attempt will be made to complete an early termination visit.

The investigator has the right to withdraw subjects from the study if a subject:

- Is in significant violation of the protocol
- Experiences an intolerable AE or SAE
- Is non-compliant
- Withdrawal of consent
- Lost to follow up
- Death

